4.0 Investigational Plan

.1 Study design: Double blinded randomized, controlled study.

.2 Methods:

.2.1 Size of study groups The primary endpoint is the incidence of non-reassuring fetal heart rate tracings after the placement of CSE. Group sample sizes of 162 in each of two groups 80% power to detect an effect size (W) of 0.1560 using a 1

degree of freedom Chi-Square Test with a significance level (alpha) of 0.05000. The incidence of fetal heart rate changes was estimated based on data from Kinsella, et al (11). The proportion of subjects with adverse fetal heart rate changes in the low-oxytocin and fluid bolus treatment group is estimated to be 8%, Therefore 350 patients will be enrolled to account for patient drop-out or ineligibility.

.2.2 Subject entry, exclusion and dropout criteria: Healthy nulliparous or multiparous women with a term ($37 \geq$ week gestation), singleton pregnancy in spontaneous labor or with spontaneous rupture of membranes, who request neuraxial analgesia, and who receive oxytocin augmentation per institutional protocols, will be eligible to participate in the study. Maternal exclusion criteria will include the presence of any systemic disease (e.g., diabetes mellitus, hypertension, preeclampsia); use of chronic analgesic medications; prior administration of systemic opioid labor analgesia; non-vertex presentation; scheduled induction of labor; or any contraindication to neuraxial analgesia.

.2.3 Protocol specific methods: Eligible women will be asked to participate shortly after admission to the Labor & Delivery Unit at Prentice Women’s Hospital during the routine pre-anesthetic interview. Informed, written consent will be obtained. Randomization based on a computer generated random number table; group assignments will be concealed in sealed, opaque envelopes. At the time of request for labor analgesia, group assignment will be determined by opening an opaque envelope. Patients will be randomized to one of two groups:

Group Assignment		Oxytocin Regimen
A		Routine oxytocin
B		Half-dose oxytocin

Fluid Management:

For patients in Groups A or B, an intravenous bolus of 500 mL LR will be initiated when the patient is positioned for CSE placement by the L & D nurse. The bolus will be administered through a free-flowing wide open intravenous catheter until complete.

Oxytocin Management:

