Neonatal data: 1- and 5-minute Apgar scores; fetal umbilical cord gases (if taken); birth weight; neonatal sepsis workup or ICU admission.

Fetal heart rate tracing data: see appendix

.2 Data evaluation:

The primary endpoint is the incidence of non-reassuring fetal heart rate tracings during the first 60 minutes after the placement of CSE. Cross tabulation tables will be constructed with the presence or absence of the endpoint as rows and the groups as columns. Differences in the frequency among groups will be assessed using a X^2 statistic. Exact tests will be computed using Monte-Carlo sampling of 10,000 samples with a confidence level of 99%. An interim data analysis will be conducted after completion of the first 175 evaluable participants.

Secondary outcomes and demographics: Age, height, weight, gestational age, fetal station, and frequency of contractions will be compared using ANOVA or Kruskal Wallis ANOVA with post-hoc comparisons correction for multiple comparisons. Binominal and ordinal data will be compared between groups using the X^2 statistic or the Fisher's exact test. A $P < 0.05$ will be required to reject the null hypothesis.

6.0 Interpretation of Anticipated Results:

We anticipate that the lower dose of oxytocin will cause fewer adverse fetal heart rate

changes in the first 60 minutes following initiation of labor analgesia.

7.0 Budget:

- .1 Materials:** No additional materials will be required as all of the materials used in the study are routinely used in the management of patients.
- .2 Labor Requirements:** Existing anesthesia personnel on Labor & Delivery Unit.
- .3 Presentation Cost:** Anticipated presentations at MARC, SOAP and ASA meetings.

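### The interim analysis at 175 participants has no stated purpose, stopping rule or alpha allocation; if the groups were tested at 0.05 at both looks, overall type I error would be about 8.2% to 8.3% by chi-square, or about 5.5% to 6.6% by the exact test at event rates of 8% to 23%

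*Combined protocol and SAP*

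**What the plan says.** The only statement on the interim is in section 5.0 Data Analysis, .2 Data evaluation: "An interim data analysis will be conducted after completion of the first 175 evaluable participants". It gives a time point and nothing else. The plan does not say what the look is for (efficacy, futility, safety or sample-size review), which endpoint is examined, who sees the result, what would stop the trial, or how the final test would be adjusted.

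The sentence ends the paragraph that defines the primary analysis. Just before it come "Differences in the frequency among groups will be assessed using a X^2 statistic" and "Exact tests will be computed using Monte-Carlo sampling of 10,000 samples with a confidence level of 99" (percent).

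Section 4.0, .2.1 Size of study groups, describes a single test: "Group sample sizes of 162 in each of two groups 80% power to detect an effect size (W) of 0.1560". The primary alpha is fixed in the same place, where the calculation is said to rest on a 1 "degree of freedom Chi-Square Test with a significance level (alpha) of 0.05000". Enrolment is then raised for attrition: "Therefore 350 patients will be enrolled to account for patient drop-out or ineligibility". Nothing there allows for a second look or for early stopping.

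The other decision threshold, "A $P < 0.05$ will be required to reject the null hypothesis", stands at the end of the secondary-outcomes paragraph in section 5.0. The only multiplicity correction mentioned is for post-hoc comparisons in that same paragraph.

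**The concern.** An interim placed inside the primary-endpoint paragraph, straight after the test is described, is easily carried out as a run of that test on the first 175 participants. If a result below 0.05 could be claimed then, and the final test were also run at 0.05, the null hypothesis would have two chances to be rejected and the stated 5% would not be held.

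The gap also matters if the trial succeeds. Under the plan's own effect size, an interim P < 0.05 would be close to an even chance (step 5 of the working). The plan does not say whether the trial would then stop, continue or report. If that is decided after the data are seen, the final p-value has no defined error rate.

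**Working it through.** **Inputs.** From section 4.0, .2.1: alpha 0.05 on a 1-df chi-square test (two-sided by construction), 162 per group (324 in total), W = 0.156, 8% events in the low-oxytocin group, 350 enrolled. From section 5.0, .2: one interim at 175 evaluable participants, chi-square statistic, Monte-Carlo exact tests. From the Background in section 2.0: reported incidence of 3% to 23%, used as the range of event rates.

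**Assumptions.** The final analysis is at 324 or, if everyone enrolled is evaluable, at 350. The interim split is taken as 88/87. Section 4.0, .2.3 says only "Randomization based on a computer generated random number table", with no blocking, so 80/95 is also tried.

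**1. The plan's own figure.** Noncentrality = N × W² = 324 × 0.156² = 7.885. The power of a 1-df chi-square test at 0.05 is 80.2%. Inversely, N = (1.960 + 0.842)² / 0.156² = 322.5, or about 162 per group. The stated 80% is reproduced, and it is a single-look calculation.

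**2. Two looks at 0.05, normal theory.** The two z-statistics have correlation √t, where t is the information fraction. Overall error = 1 − P(|Z₁| ≤ 1.96 and |Z₂| ≤ 1.96).
- t = 175/324 = 0.540, √t = 0.735: 8.17%.
- t = 175/350 = 0.500, √t = 0.707: 8.31%.

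**3. Full binomial enumeration, 88/87 at the interim.** Probability under the null that either look gives p < 0.05:

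| Event rate | Chi-square, N = 324 | Exact, N = 324 | Chi-square, N = 350 | Exact, N = 350 |
|---|---|---|---|---|
| 3% | 7.5% | 3.1% | 7.7% | 3.2% |
| 5% | 7.9% | 4.5% | 8.0% | 4.7% |
| 8% | 8.2% | 5.6% | 8.4% | 5.7% |
| 13.3% | 8.3% | 6.1% | 8.5% | 6.4% |
| 18.6% | 8.2% | 6.3% | 8.4% | 6.4% |
| 23% | 8.1% | 6.3% | 8.3% | 6.5% |

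The exact test is conservative: at rates of 8% to 23% its final look alone has an error of only 3.0% to 3.7%. That is why the second look takes it only modestly above 5%.

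**4. Sensitivity to the split.** With 80/95 at the interim and N = 324, the same six rates give 6.8% to 8.2% by chi-square and 3.9% to 6.4% by the exact test. At a 5% event rate the exact error is 5.05% (N = 324) or 5.24% (N = 350). At low event rates, whether the exact test stays under 5% therefore depends on the split. Simulation with the 88/87 split gave 5.5% to 6.6% for the exact test at rates of 8% to 23%.

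**5. Chance of an interim P < 0.05 under the planned effect.** √175 × 0.156 = 2.064, and Φ(2.064 − 1.960) = 54%.

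**6. Boundaries that hold 5%.** O'Brien-Fleming-type spending of 0.05 two-sided gives an interim level of 2[1 − Φ(1.960/√t)]. The final level is then solved so that the overall error is 5%.
- 175/324: 0.0077, then 0.0470.
- 175/350: 0.0056, then 0.0478.

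An interim level of 0.001 followed by an unadjusted 0.05 gives 5.02% at either fraction, just over the target. The final level that holds 5% is 0.04982 at 175/324 or 0.04978 at 175/350, about 0.0498.

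**7. Power with the boundary.** At N = 324 with the 0.0077/0.0470 pair, normal-theory power is 79.7%, against 80.2% for the single test.

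**The case against.** The strongest reply is that the inflation is hypothetical. The plan never says that the groups will be compared at 175 or that success could be claimed there. Section 4.0 has 350 patients enrolled, with no provision to stop early. On a literal reading, enrolment runs to the end and one test at 0.05 is made, which by itself holds about 5%. A safety-only look, or a blinded look at the pooled event rate, would add nothing to the error. This stands: a reader might infer that the trial has an 8.2% type I error, and the documents do not support that. They support only the statement that the plan leaves this use of the interim open.

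The second reply is that the exact test removes the problem. Section 5.0 can be read as one chi-square statistic whose p-value comes from Monte-Carlo sampling, or as an asymptotic test with separate exact tests. On the first reading the relevant figure is about 6%, not 8%, and it is near or below 5% at low event rates. This stands in part. At the plan's own 8% and above, the exact error still exceeds 5%. It would also be too strong to say that the exact test is safe at every rate below some fixed value, because that changes with the interim split.

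The third reply is that the P < 0.05 sentence belongs to the secondary outcomes. It does, and it should not be read as an interim threshold. The argument does not need it, since the primary alpha is set in section 4.0.

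**Conclusion.** The omission is certain: an interim is scheduled within the primary-endpoint paragraph, and the plan gives no purpose, stopping rule or alpha allocation while the whole 0.05 is assigned to one test. The consequence is conditional. If the groups are compared on the primary endpoint at 0.05 at both looks and either look can support a claim, overall two-sided error is about 8.2% to 8.3% by the chi-square p-value (normal theory). By the exact p-value it is about 5.5% to 6.6% at event rates of 8% to 23%, and near or below 5% at 3% to 5%, depending on the interim split. Without an efficacy use of the interim there is no inflation.

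The figures rest on a final analysis at 324 or 350 and, for the enumerations, on assumed interim splits. This should be fixed before the interim takes place; it does not show that the final test is invalid.

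**What to change.** Before the interim is run, add one of the following to section 5.0, .2 Data evaluation.

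1. **Prespecify a boundary that holds two-sided 5% overall.** One example is O'Brien-Fleming-type spending of 0.05 two-sided: interim p < 0.0077 and final p < 0.0470 at 175/324, or 0.0056 and 0.0478 at 175/350. Another is interim p < 0.001 with final p < 0.0498. State which p-value, Monte-Carlo exact or asymptotic chi-square, is compared with the boundary.
2. **State that the interim makes no between-group efficacy comparison and cannot support an efficacy claim.** The final test then keeps its full 0.05.

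The cost is two or three sentences and no added patients. Under option 1 with the O'Brien-Fleming-type boundary, normal-theory power at 324 falls from 80.2% to about 79.7%. Under option 2 it is unchanged.

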There are many factors that contribute to alterations in the fetal heart rate including stage of labor, fetal head compression, cord compression, and uteroplacental insufficiency. Oxytocin is used in labor and delivery to increase the frequency of contractions and augment uterine contractile strength, thereby establishing a regular pattern of labor. However, the administration of exogenous oxytocin in the presence of an uncoordinated labor pattern confers a risk for increase in uterine contraction frequency, resulting in inadequate relaxation periods. This leads to an increase in the basal tone of the uterus, which may lead to a tetanic contraction with risk decreased uteroplacental blood flow and fetal hypoxemia (3,4). Since the introduction of oxytocin for labor induction in 1948, there have been multiple protocols for the administration of oxytocin, both for labor induction, as well as for augmentation of labor. Many institutions use an active management of labor protocol (AMOL) to facilitate labor and delivery through oxytocin management. Use of the AMOL protocol decreases the duration of labor and the Cesarean delivery rate for dystocia (5). The evidence is divided as to the effect of high- versus low-dose oxytocin administration on fetal heart rate abnormalities (6-10). Merrill et al. randomized patients to low- versus high-dose oxytocin for augmentation or induction of labor (9). Oxytocin was decreased or discontinued more commonly in the high-dose group, both for uterine hyperstimulation and FHR abnormalities. In contrast, a study comparing high-dose oxytocin management with standard care found that there were no differences in fetal outcomes or the incidence of fetal distress between groups (10). One of the limitations of the previous studies is that the labor analgesia was not standardized; and consisted of either traditional epidural (high dose) analgesia or

intravenous opioids. Labor analgesia itself has been implicated as a cause of non-reassuring fetal heart rate tracings. The combination of low-dose combined spinal epidural analgesia and the high-/low-dose oxytocin have not been evaluated.

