One of the proposed mechanisms for non-reassuring fetal heart tracings after initiation of analgesia is that the pain relief from neuraxial analgesia causes a decrease in catecholamine release by the sympathetic nervous system (5). The subsequent decrease in the circulating epinephrine concentration contributes to an increase in uterine tone, as epinephrine is a potent tocolytic agent. The increased tone, in turn, leads to a decrease in placental blood flow, and eventually fetal bradycardia.

The optimal oxytocin management in the peri-analgesia initiation period in terms of effects on uterine activity, uteroplacental perfusion, and fetal oxygenation, is not known. Anecdotally, some institutions arbitrarily decrease (or do not increase) the oxytocin infusion rate during initiation of analgesia. We hypothesize that decreasing the oxytocin infusion rate immediately before the initiation of CSE analgesia will cause fewer adverse fetal heart rate changes in the first 60 minutes following initiation of labor analgesia compared with maintaining the infusion rate.

3.0 Literature:

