The Prentice Women's Hospital oxytocin augmentation protocols will be used. At the time of request for analgesia, if the patient is in group A the oxytocin management will continue as per the normal oxytocin protocol.

If the patient is randomized to groups B the dose of oxytocin currently being administered will be halved and not increased for the duration of the study period (60 minutes after the initiation of CSE). Care providers other than the Labor & Delivery nurse managing the fluid and oxytocin infusions, will be blinded to group assignment.

Analgesia Management:

All subjects will receive a maintenance infusion of 125 mL lactated Ringers (LR) solution throughout the study period as per Labor and Delivery protocol. Per institutional protocol, all patients will receive a 500 mL bolus of LR solution at the start of the neuraxial procedure ("wide-open rate") via the mainline IV. Labor analgesia will be initiated in the sitting position at the L3-4 or L2-3 interspace with a routine combined spinal-epidural (CSE) technique. The epidural space will be located with the loss of resistance technique and a 27-g x 5-in pencil point spinal needle will be passed through the epidural needle to the subarachnoid space. The intrathecal injection will consist of bupivacaine 2.5 mg and fentanyl 15 µg. A 20 gauge epidural catheter will be threaded and secured 4-5 cm in the epidural space. A test dose of 3 mL lidocaine 1.5% with epinephrine 1:200,000 will be administered through the epidural catheter. The epidural catheter will be

secured and the patient will be positioned in a lateral recumbent position. Patient-controlled epidural analgesia (PCEA) infusion of bupivacaine 0.0625% with fentanyl 1.95 µg/mL will be started at a rate of 8 mL/h with bolus dose = 8 mL, lock-out interval = 10 min and maximum volume = 32 mL/h.

Fetal heart rate monitoring:

Fetal heart rate monitoring and frequency of uterine contractions will be recorded by external tocodynamometry.

Treatment of hypotension:

Any decrease of 10% or greater from baseline in maternal systolic blood pressure after placement of the CSE will be treated by the IV administration of ephedrine or phenylephrine as guided by maternal heart rate, as per standard practice.

Treatment of non-reassuring fetal heart rate changes:

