If there are prolonged fetal heart rate decelerations, recurrent late decelerations, severe variable decelerations, or tachysystole, the Prentice Women's Hospital protocol for oxytocin management and intrauterine resuscitation will be followed.

Study completion:

The study is complete after 60 min after the intrathecal injection. After this time, obstetric and anesthesia management, including fluid and oxytocin management, will not be dictated by study protocol.

Fetal heart rate tracing assessment:

Fetal heart rate tracings will be examined for 30 minutes before and 60 minutes after the initiation of analgesia by a perinatologist blinded to study group off-line after delivery. NICHD guidelines (13) will be used to assess FHR patterns. Non-reassuring FHR patterns will be defined as any one or more of the following: minimal or absent variability, late decelerations, and persistent deceleration (see

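### Contraction frequency has no stated time window and is compared without the woman's own pre-allocation value; a baseline-adjusted analysis would be more precise, provided the baseline ends before the oxytocin change

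*Combined protocol and SAP*

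**What the plan says.** Section 5.0 .2 (Data evaluation) treats secondary outcomes and demographics in one sentence. After age, height, weight and gestational age it continues: "fetal station, and frequency of contractions will be compared using ANOVA or Kruskal Wallis ANOVA". It names no covariate, change score or repeated-measures model, and it does not say over which minutes contraction frequency is counted.

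Three parts of section 4.0 .2.3 bear on what could be used.

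- Fetal heart rate monitoring: "Fetal heart rate monitoring and frequency of uterine contractions will be recorded by external tocodynamometry".
- Reading of the tracing, under its own subheading: "Fetal heart rate tracings will be examined for 30 minutes before and 60 minutes after the initiation of analgesia". The reader, a perinatologist, does not know the group.
- Allocation and treatment: "At the time of request for labor analgesia, group assignment will be determined by opening an opaque envelope". In group B, "the dose of oxytocin currently being administered will be halved and not increased for the duration of the study period".

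Section 5.0 .1 leaves the list of tracing variables to an attachment: "Fetal heart rate tracing data: see appendix". That appendix is not in the text available for this review. Its absence here is not a fault of the plan.

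The Background in section 2.0 explains why uterine activity matters. Giving oxytocin when labor is uncoordinated "confers a risk for increase in uterine contraction frequency, resulting in inadequate relaxation periods", and the fall in epinephrine after analgesia "contributes to an increase in uterine tone, as epinephrine is a potent tocolytic agent".

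**The concern.** Of the variables in that sentence, contraction frequency is the only one that halving oxytocin could plausibly change. The others are characteristics of the woman or the pregnancy, or are examined before the CSE. It is also the only direct measure of uterine activity named in the Data evaluation section. It nevertheless receives the same treatment as height and weight.

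Two things follow.

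1. **The window is undefined.** If the line means the pre-CSE frequency, it is a comparability check and the effect of treatment on contractions is not tested. If it means the post-CSE frequency, it is an outcome and should be defined as one.
2. **If it is an outcome, available information is left out.** A woman's frequency before allocation probably predicts her frequency afterwards. A one-way ANOVA leaves that predictable variation in the error term, and Kruskal-Wallis in its standard form takes no covariate.

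What is at stake is the precision of a secondary comparison. If the primary result is null, this comparison would help to show whether the intervention changed contraction frequency at all.

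**Working it through.** **Step 1. The plan's own figure.** Section 4.0 .2.1 gives 162 per group (324 in total), W = 0.1560, alpha 0.05 and 80% power for the 1-df chi-square test. The noncentrality is N × W² = 324 × 0.1560² = 7.885, which gives power 0.802. The figure reproduces, but it concerns the binary primary endpoint. No SD, effect size, power or correlation is stated for contraction frequency.

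**Step 2. Unadjusted comparison of contraction frequency.** Take 162 per arm and two-sided alpha 0.05. The difference detectable with 80% power is (1.960 + 0.842) × √(2/162) = 2.802 × 0.1111 = 0.311 SD.

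**Step 3. Adjustment for a clean baseline.** With pre/post correlation r, ANCOVA multiplies the error variance by 1 − r². At the difference from Step 2:

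power = Φ(2.802/√(1 − r²) − 1.960)

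The values of r are assumptions.

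| r (assumed) | 1 − r² | Power | Detectable difference (SD) | Equivalent n per arm, 162/(1 − r²) |
|---|---|---|---|---|
| 0 | 1.00 | 80.0% | 0.311 | 162 |
| 0.2 | 0.96 | 81.6% | 0.305 | 169 |
| 0.3 | 0.91 | 83.6% | 0.297 | 178 |
| 0.5 | 0.75 | 89.9% | 0.270 | 216 |
| 0.7 | 0.51 | 97.5% | 0.222 | 318 |

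**Step 4. Which minutes can serve as baseline.** The 30-minute window is anchored to the initiation of analgesia, but the envelope is opened at the request for analgesia and group B's oxytocin is reduced before the CSE. Part of the window can therefore follow the change. The documents do not give the interval, so the overlap is unknown.

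Suppose a share c of the window follows the change and carries the same effect, with equal SDs before and after (assumptions). The adjusted estimate then keeps a fraction 1 − r × c of the effect, and:

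power = Φ(2.802 × (1 − r × c)/√(1 − r²) − 1.960)

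| r | c | Effect kept | Power |
|---|---|---|---|
| 0.3 | 0.25 | 92.5% | 77.5% |
| 0.5 | 0.25 | 87.5% | 80.8% |
| 0.5 | 0.50 | 75.0% | 67.9% |
| 0.7 | 0.50 | 65.0% | 72.2% |

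So adjusting for the whole pre-CSE window can do worse than not adjusting, and it also biases the estimate toward zero. The gains in Step 3 hold only for a baseline that ends before allocation.

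**Step 5. Whether that baseline can be identified.** Section 5.0 .1 collects the time of intrathecal injection and the start and stop of the fluid bolus. It lists no time for the request, the envelope opening or the oxytocin change. Without one of these, the pre-allocation minutes cannot be marked on the tracing. Where the interval from request to CSE reaches 30 minutes, the window as planned contains no such minutes.

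**The case against.** The strongest reply is that the line may be only a baseline comparison. Contraction frequency stands among baseline items, no window is given, and the missing appendix might define separate pre and post values. That stands as far as it goes: the text does not establish that a post-CSE outcome was meant, nor that contraction frequency is extracted for both periods. It does not remove the point, because on the baseline reading the plan names no direct test of contraction frequency after treatment. Even if the appendix defines the windows, the analysis sentence still uses no covariate.

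It is also fair to say that the unadjusted comparison is unbiased, that its standard error already allows for chance imbalance, and that the gain rests on an undocumented correlation. All of this stands. At r of 0.2 to 0.3 the gain is less than 4 percentage points of power.

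A reader might go further than the documents allow in three ways.

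- **That precision is discarded for no reason and could be recovered from data already in hand.** The plan does not record the time needed to separate minutes before and after allocation, and the full pre-CSE window is not a clean baseline.
- **That contraction frequency is the trial's mechanism outcome.** The plan never calls it that. The Background's account of what follows analgesia runs through uterine tone, and frequency is one link in the wider chain. Section 5.0 .1 also collects how often oxytocin is stopped or decreased for hyperstimulation or non-reassuring fetal status, which bears indirectly on uterine activity.
- **That women enter at widely differing frequencies.** The documents give no figures on this.

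**Conclusion.** The point holds as one of definition and precision on a secondary measure. Contraction frequency has no stated window, and its planned test uses no pre-allocation value. With a clean baseline and any correlation above zero, ANCOVA would be more precise. At 162 per arm it would raise 80% power to about 82% at r = 0.2, 84% at 0.3, 90% at 0.5 and 97.5% at 0.7. These figures assume a baseline untouched by treatment, a roughly linear relation and complete data. The documents supply no value of r, so no single figure can be given for the loss. The planned test is not invalid, and the primary endpoint and sample size are unaffected.

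**What to change.** In section 5.0 .2, take contraction frequency out of the list of demographics and specify it as follows.

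- **Outcome:** mean contractions per 10 minutes over the 60 minutes after CSE.
- **Analysis:** ANCOVA on arm and on the woman's frequency in the tracing minutes before the envelope was opened, in a rank-based version if the data are skewed.
- **Report:** the adjusted difference between arms with its 95% CI.
- **Baseline window:** state that it ends before the envelope is opened, and that the full 30 minutes before CSE is not used as the covariate.

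In section 5.0 .1, add the time of envelope opening or of the oxytocin change. In the tracing assessment, state that contractions are counted in both windows, unless the appendix already does so.

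The cost is a few lines of text, one extra recorded time and, where the interval from request to CSE uses up the 30 minutes, reading a somewhat earlier stretch of tracing. No additional participants are needed. The text should be settled before group comparisons are seen, including those at the planned interim analysis, so that the choice among post values, change scores and adjusted values is not guided by the data.
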